4 STUDY DESIGN

This is a multicenter, Phase IV, cluster randomized trial to determine whether an intensive intervention of COHS's administering FV (offered 4x a year) and OHP for 2 years in an AI population of children ages 3-6 years in HSCs on the Navajo Reservation vs. usual oral health care made available by the IHS dental providers will reduce the dmfs measure in the children. A cluster randomized design was chosen to reduce the potential for contamination between the 2 intervention groups.

There are approximately 96 HSC classrooms in the NN (based on 2011-2012 school year). We will stratify HSCs on the basis of population size, and randomly assign the HSC classrooms to the 2 arms of the study within the strata. This will make the number of children in each of the 2 arms of the study approximately equal.

The intensive intervention group will have the specially-trained COHS administer FV to the children 4x a year and provide OHP to the parents/caregivers and to the children in the HS classrooms, for 2 years. The other randomized group will have usual oral health care made available by the IHS Dental providers or other community providers.

Enrollment of HSCs will be done over a period of 6 months (in each year, year 1 and year 2). Upon parental consent of the child and parent/primary caregiver consent for her/himself, the HS children from each HSC classroom will be enrolled in the study. Each consented child will participate in the study for up to 3 years. A baseline assessment of the dmfs measure for each child will be done (objective 3.1.1.3 and 3.1.2.1/ outcome 3.2.1 and 3.2.2.1), and a baseline assessment of the dental knowledge, attitudes, and behaviors of the parents/caregivers (objectives 3.1.2.2 and 3.1.2.3/ outcome 3.2.2.2 and 3.2.2.3). The interventions will be administered for 2 years in the Head Start classrooms. The number of interventions a participating child receives will vary with the length of time that the child attends the Head Start class. Annual assessments of the dmfs measure for the children and the dental knowledge, attitudes, and behaviors of the parents/caregivers will be made for 3 years. The 3rd annual assessment is included to determine changes in the outcome measures for up to 18 months after the FV and OHP have ended, to assess the longer term effects of the intervention.

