The primary outcome of the study will be changes from baseline in dmfs (dmfs increment at two and three years) between the 2 groups. Secondary outcomes will include possible changes in caries patterns, and potential moderators/mediators of treatment effect such as parental knowledge, attitudes and behaviors, and the cost of each of the two intervention conditions.

The dmfs measures (objective 3.1.1.3 and 3.1.2.1/ outcome 3.2.1 and 3.2.2.1) will be made by oral screening of the children, to be completed by calibrated dental hygienists who will visit each HSC in both the COHS intervention (Group 1) and the Usual Care (Group 2) arms.

Questionnaires, known as the Basic Research Factors Questionnaire (BRFQ) or Audio Computer Assisted Survey Interview (ACASI) survey, of dental knowledge, attitudes, behaviors and service utilization (objectives 3.1.2.2 and 3.1.2.3/ outcome 3.2.2.2 and 3.2.2.3) will be completed by the parents/caregivers annually, and the data will be entered into laptop computers. We will follow the families whose children age out of Head Start and make arrangements for them to complete the child oral health screening and parent questionnaires at a convenient time and location. All data collected on laptops in the field will be sent first to UCD and then uploaded to the central statistical coordinating center.

NIDCR has appointed a Data Safety and Monitoring Board to provide oversight of the studies and review of interim analyses for all ECC projects in the consortium.

A Manual of Procedures (MOP) has been created to detail the conduct and operations of the study. It transforms the study protocol into a guideline that describes all aspects of the study's organization, operational definitions, recruitment, screening, enrollment, randomization, intervention, follow-up procedures, data collection methods, data tracking and transfer, case report forms (CRFs), and quality control procedures.

The MOP is a dynamic document that will be updated throughout the study to reflect any amendments to the protocol, participant consent forms, CRFs and study procedures. The MOP will be submitted once a year at continuing review unless it requires a change in the protocol. At continuing review, tracked changes and a summary of updates to the MOP made throughout the year will be submitted.

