8 STUDY PROCEDURES/EVALUATIONS

8.1 Clinical Evaluations

All children in the study will be provided an oral health screening at baseline and annually thereafter for 3 years (up to 4 screenings total). The oral health screening will collect dmfs measures (objective 3.1.1.3 and 3.1.2.1/ outcome 3.2.1 and 3.2.2.1) of the children, to be completed by calibrated dental hygienists who will visit each HSC in both the COHS intervention (Group 1) and usual care (Group 2) arms. Procedures for the oral health screening will be followed according to the protocol of the Caries Outcome Work Group of the ECC consortium. The Caries Outcome Work Group will develop an SOP for the oral health screenings, which will be attached to this protocol. The criteria for the determination of dmfs measures according to Drury, et al.²⁸ will be used. These criteria include the counting of both non-cavitated and cavitated carious lesions.

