10.2 Sample Size Considerations

Sample size is based upon the following assumptions:

1. The primary outcome measure is dmfs, measured at baseline and annually for three years after the beginning of the intervention when the HS children ages 3-5 at enrollment (or possibly 6, depending on the timing of enrollment) will be ages 6-8 (or possibly 9).
2. The test statistic used is the t-test for 2 independent samples, with an inflation factor for the cluster randomized design.^{29, 30}
3. The null hypothesis is no difference in the mean dmfs between the 2 randomized groups 2 years and 3 years after the beginning of the intervention when the children are 5-7 6-8 (or possibly 9) years old. The alternative hypothesis is that there is a difference.
4. Type I error rate will be set at 0.05
5. Type II error rate will be set at 0.20 (Power = 0.80)
6. From the 1999 IHS oral health survey ⁵, the average dmfs for AI children ages 5-7 was 18.55. It was also observed that Navajo children tended to have dmfs measures about 30% higher than the national average for all AI children. Therefore, it was assumed that the average dmfs for Navajo children ages 5-7 will be about 24 under conditions of usual care, with a standard deviation of about 24. We also assumed a 40% reduction in this average dmfs measure for group 1.
7. Based on the experience of other studies the Centers for American Indian and Alaska Native Health have conducted with AI communities, a 70% retention rate was assumed.

8. If subjects drop out of the study due to adverse effects or other reasons, we will ask them to continue in the follow-up even if treatment is discontinued, so that we can perform an “intention to treat” analysis. The “intention to treat” analysis will be the primary analysis of the study.
9. We also assumed an average HS class size of about 20 children and an intraclass correlation of about 0.045, considered to be an appropriate intraclass correlation.³¹

On the basis of the assumptions above, we calculate a need to randomize 52 HSC classrooms, or about 26 HSC classrooms in group 1 and 26 HSC classrooms in group 2. This means that we will need to enroll about 1040 children, or 520 children in group 1 and 520 children in group 2. Sample size calculations are shown in the table in *Appendix B*.

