10.4 Final Analysis Plan

The primary outcome measure will be the difference between groups 1 and 2 on the changes in mean dmfs between baseline and 2-year and 3-year follow-up. Descriptive statistics will be examined first to yield important information about the most appropriate analysis strategies. If the change scores for dmfs are not normally distributed, a log transformation can be made, or a non-parametric test can be used. Longitudinal methods of analysis will be used to examine these repeated, correlated observations within subjects over time.^{32, 33} Other models such as negative binomial regression, mixture models such as ZIP and ZINB will be considered.

Exploratory analyses will first be done to evaluate the trends in the data to determine the most appropriate mean and covariance structures for the data. Graphical displays will be used to assess the mean structure for modeling fixed effects, including scatter plots of the response variable versus time, plots of individual subject profiles, plots of mean profiles, and smooth curve fits to the data. Simple plots of individual subject profiles (dmfs over time) can be very revealing and show whether there is heteroscedasticity in the data (fanning of the curves with time).

Linear mixed models will be used because they can incorporate both fixed and random (subject-specific) effects and permit different covariance structures. A typical example (“random regression”) allows each subject an individual time trend, and treatment effects may cause differences in slope over time. The within-subjects autocorrelation is assumed to be due to these individual trends, on top of which is superimposed independent measurement errors. When analyzing randomized trials, it is assumed that the responses are the values that occur after randomization, because they are influenced by treatment. Thus, it is customary in such trials to consider the baseline value as a covariate, rather than as a response variable. The randomization of subjects in groups or clusters (i.e., HSCs) can also be accounted for in the mixed model with a random effect for group.

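### The 2-year and 3-year dmfs changes are both primary under a single alpha of 0.05, and no contrast or rule decides success; the log option for change scores also cannot be computed at zero or below

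*Combined protocol and SAP*

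**What the plan says.** Three places in the combined protocol and SAP define the primary comparison, and each names two times.

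- Section 4 (Study Design) gives the primary outcome as change from baseline, specified as "dmfs increment at two and three years".
- Section 10.2 (Sample Size Considerations) states the null hypothesis as "no difference in the mean dmfs between the 2 randomized groups 2 years and 3 years after the beginning of the intervention". It is written on mean dmfs, not on change, and the alternative is non-directional. The same list says "Type I error rate will be set at 0.05", once, with no division between times.
- Section 10.4 (Final Analysis Plan) defines the primary outcome as "the difference between groups 1 and 2 on the changes in mean dmfs between baseline and 2-year and 3-year follow-up".

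Section 4 also explains that the third annual assessment is there "to assess the longer term effects of the intervention". This suggests that 2 years comes first, but no order of testing follows from it.

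On method, section 10.4 commits to longitudinal analysis with linear mixed models, describes baseline as customarily a covariate, and says that a random effect can account for the randomization of centers. It also offers this fallback: "If the change scores for dmfs are not normally distributed, a log transformation can be made, or a non-parametric test can be used". Negative binomial and zero-inflated models are to be considered as well. On scoring, section 8.1 says of the caries criteria: "These criteria include the counting of both non-cavitated and cavitated carious lesions".

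**The concern.** With two primary times and one alpha, the plan has to say what counts as a positive trial. It does not. If the groups differ at 2 years but not at 3, or the reverse, the result could be reported as success or as failure without departing from the text. Section 10.4 adds to the uncertainty: its mixed-model example has treatment acting on the slope over time, a third possible deciding contrast. What is at stake is how the main result is declared and whether the stated 0.05 is the error rate that applies.

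The log option is a smaller, separate fault. A child with no new affected surfaces has a change of zero. Negative changes are possible too, because non-cavitated lesions are counted and a repeat screening may score lower. The logarithm does not exist for either. The same paragraph considers zero-inflated models, so zeros are expected.

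**Working it through.** **Inputs.** Two primary times (sections 4, 10.2, 10.4). Alpha 0.05, two-sided because the alternative is non-directional (section 10.2), so the critical value is 1.96. The correlation ρ between the 2-year and 3-year test statistics is not in the documents; I assume 0.5, 0.7 and 0.9.

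**Step 1: one joint test.** A single test of the group effect over both times has type I error 0.05. This reproduces the plan's figure, so the plan's alpha is attainable under one reading.

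**Step 2: each time at 0.05, success on either.** Under the null, with (Z₂, Z₃) bivariate normal with correlation ρ:

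error = 1 − P(|Z₂| < 1.96 and |Z₃| < 1.96)

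| ρ (assumed) | P(neither significant) | Either-time error |
|---|---|---|
| 0.5 | 0.9093 | 0.0907 |
| 0.7 | 0.9165 | 0.0835 |
| 0.9 | 0.9296 | 0.0704 |

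The limits are 1 − 0.95² = 0.0975 at ρ = 0 and 0.05 at ρ = 1. A simulation with 26 classes per arm, 14 children per class, ICC 0.045 and a t-test on class means (200,000 runs) gave 0.0906, 0.0836 and 0.0714.

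**Step 3: fixed sequence, 2 years then 3 years.** If both nulls hold, an error requires the 2-year test to reject, which has probability 0.05. If only the 3-year null holds, an error requires the 3-year test to reject, which has probability at most 0.05. The familywise error is therefore at most 0.05 for any ρ. The same simulation gave 0.0498, 0.0500 and 0.0500.

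**Step 4: cost in power.** The first test in the sequence keeps the whole 0.05, so its power is what a single test at 2 years would have. For scale only, from section 10.2:

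- Difference 0.40 × 24 = 9.6; SD 24; retained per arm 520 × 0.70 = 364.
- Design effect 1 + (m − 1) × 0.045, which is 1.855 for m = 20 and 1.585 for m = 20 × 0.70 = 14.
- SE = 24 × √(2 × DE / 364), which is 2.423 and 2.240.
- Power = Φ(9.6/SE − 1.96) = Φ(3.962 − 1.96) = 97.7% and Φ(4.286 − 1.96) = 99.0%.

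These figures are at classroom level and for dmfs level. Section 5.3.1 randomizes centers of one to three classes, and the primary outcome is change, so they are not the power of the primary analysis.

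**Step 5: log option.** For change c = follow-up dmfs − baseline dmfs, log(c) exists only if c > 0. Section 10.4 gives no offset and no rule for c ≤ 0, so the option cannot be run on those children as written.

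**The case against.** The best defence is that section 10.2 writes one null at one alpha, and section 10.4 commits to longitudinal models. Together these fit a single joint test at least as well as two separate tests, and a joint test holds 5%. Two tests with a win at either time are nowhere proposed. This stands as far as it goes: a reader might infer that the trial's error rate is 7–9%, and the documents do not support that. It does not remove the gap, because section 10.4 names no joint contrast, section 10.2 sizes the trial on a two-sample t-test, and no text excludes the either-time reading.

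On the log option, a reader might infer that children with undefined values would be dropped, contrary to section 10.2, where the intention-to-treat "analysis will be the primary analysis of the study". Nothing in section 10.4 proposes dropping them. The log is one option among several, and an offset is an ordinary remedy. The point is limited to an undefined calculation; no bias figure can be attached to it.

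A reader might also infer from the word 'can' that clustering may be ignored. That is not supported either. Section 10.2 applies a cluster inflation factor, section 10.4 names the random effect, and no unclustered analysis is proposed. Only a wording edit is warranted.

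**Conclusion.** The concern holds as a missing decision rule. Two times are primary under one alpha, and the contrast that decides the trial is not named. The type I error is 5% under a joint test and about 7–9% under the either-time reading, which the plan does not rule out. That range rests on two separate two-sided tests at 0.05, success on either, and assumed correlations from 0.9 down to 0.5. The undefined log of change scores is a definite but secondary fault. Both should be corrected; neither shows that the trial is under-sized or that the planned mixed model is unsound.

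**What to change.** Before any look at outcomes by arm:

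1. In sections 10.2 and 10.4, state that the 2-year group difference is tested first at two-sided 0.05, and the 3-year difference at two-sided 0.05 only if the 2-year test is significant. This agrees with the role that section 4 gives the third assessment.
2. Take both differences from one linear mixed model of follow-up dmfs, with baseline dmfs as covariate and a Head Start Center random effect. With baseline in the model, the group difference in follow-up level equals that in change, so the section 10.2 and 10.4 wordings then agree.
3. Delete the log transformation of change scores. Replace it with a negative binomial mixed model on the follow-up count, with the same baseline and center terms.
4. Reword section 10.4 so that center clustering will be, not can be, accounted for.

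This costs only wording: no new data and no added enrolment, since the first test keeps the full alpha. The price is that a benefit seen only at 3 years could not be claimed as a primary result. The negative binomial model would also report a ratio of means in place of a difference. Any power quoted alongside should be labelled as classroom-level and based on dmfs level.

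### Section 10.4 makes the HSC term optional and names no HSC-by-time effect, so the stated 5% type I error for change in dmfs is not secured

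*Combined protocol and SAP*

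**What the plan says.** - **Randomised unit.** Section 5.3.1 randomises HSCs, stratified by number of classes (1 vs. 2-3) and by Navajo agency.
- **Primary contrast.** Section 10.4 compares the groups on change in mean dmfs from baseline to the 2-year and 3-year follow-up.
- **Error rate and clustering at the design stage.** Section 10.2 states "Type I error rate will be set at 0.05", with an alternative that is two-sided in effect ("The alternative hypothesis is that there is a difference"). It inflates the sample size for clustering, using classes of about 20 and "an intraclass correlation of about 0.045".
- **Model.** Section 10.4 plans linear mixed models. Its typical example "allows each subject an individual time trend, and treatment effects may cause differences in slope over time". The same paragraph then says that trials usually enter baseline as a covariate and not as a response.
- **Clustering in the analysis.** Randomisation by HSC "can also be accounted for in the mixed model with a random effect for group". Nothing else in section 10.4 concerns clustering. The covariance structure is to be chosen from the data. A non-parametric test, negative binomial regression and zero-inflated models are kept open, with no clustering term named for any of them.

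**The concern.** An HSC intercept moves every visit of a centre by the same amount. When baseline is one of the responses, it therefore cancels from a change score or a slope. If centres differ in how fast caries accumulates, that variation passes into the child-level terms, which the model treats as independent between children. The clustering that section 10.2 pays for in sample size would then be missing from the standard error of the primary contrast. The confidence interval would be too narrow, and a programme with no effect would be declared effective more often than 5% of the time. The permissive wording also leaves room for no HSC term at all.

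**Working it through.** **Inputs from section 10.2.** Two-sided alpha 0.05; class size 20; retention 70%, so 20 x 0.70 = 14 children per cluster; ICC 0.045; 52 classrooms.

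**Assumptions.** The documents give no ICC for change, so 0.045 is borrowed from the dmfs sample-size assumptions. The child-level variances are also assumed: intercept SD 18, with (slope SD per year, error SD) of (3, 6), (5, 5) or (7, 4).

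**The plan's own figure.** The stated size of 520 per arm does not reproduce. A mean and SD of 24 with a 40% reduction give a difference of 9.6. Then 2 x (1.96 + 0.84)^2 x (24/9.6)^2 is about 98.1, or 99 per arm; 99 x 1.855 / 0.70 = 262.4, or 263 per arm. The Appendix B table is not in the text available, so the cause cannot be traced. This does not affect the error-rate question, which depends on cluster size and ICC.

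**Step 1: clustering of change ignored altogether.** With design effect DE = 1 + (m - 1) x ICC, the true error is 2[1 - Phi(1.96/sqrt(DE))].

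| m | ICC of change | DE | Error |
|---|---|---|---|
| 14 | 0 | 1 | 5.0% |
| 14 | 0.02 | 1.260 | 8.1% |
| 14 | 0.03 | 1.390 | 9.6% |
| 14 | 0.045 | 1.585 | 12.0% |
| 20 | 0.045 | 1.855 | 15.0% |
| 28 | 0.045 | 2.215 | 18.8% |

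The last row is an HSC with two classes of 14 retained children.

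**Step 2: HSC intercept only, baseline as a response, HSC slopes vary, m = 14.** The intercept cancels, so Step 1 applies to each change. Set the ICC of year-3 change at 0.045; year-3 error is then 12.0%. For year 2, let s be the child slope SD, e the error SD and t the HSC slope variance. Then t = (0.045/0.955) x (9s^2 + 2e^2)/9, and the year-2 ICC is 4t/(4t + 4s^2 + 2e^2).

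- (3, 6): t = 0.801, ICC 0.0288, DE 1.375, error 9.5%.
- (5, 5): t = 1.440, ICC 0.0370, DE 1.481, error 10.7%.
- (7, 4): t = 2.476, ICC 0.0416, DE 1.541, error 11.4%.
- Limits: with s = 0 the ICC is 0.0205 and the error 8.2%; with e = 0 they are 0.045 and 12.0%.

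The range is therefore about 8-12%. A null simulation of the slope model agrees. It used 52 HSCs, 14 children each and 4 visits, with child intercept SD 16, child slope SD 4 per year with 4.5% of slope variance between HSCs, HSC intercept SD 4 and error SD 3. It rejected in 12.4% of 380 trials (Monte Carlo SE 1.7 points).

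**Step 3: HSC intercept only, baseline as a covariate, m = 14.** The model with unstructured child covariance was fitted to the expected moments, and its variance was compared with the true variance. ICC 0.045; ranges are over the three variance sets.

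| HSC effect over follow-up | Visits modelled | Year 2 | Year 3 |
|---|---|---|---|
| Constant | 1-3 or 2-3 | 5.0% | 5.0% |
| Grows linearly | 1-3 jointly | 7.3-11.2% | 10.2-11.9% |
| Grows linearly | 2-3 jointly | 4.3-9.3% | 7.5-10.9% |

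A slope contrast over years 1-3 with a growing HSC effect gives 9.6-11.6%.

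**Step 4: matching HSC term.** An HSC-by-visit effect, an HSC slope where time is linear, or a separate baseline-adjusted model per visit with an HSC intercept brings the error back to about 5%.

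**The case against.** A reader might infer that the plan's HSC term cannot carry centre differences in caries change, and hence that the primary test runs at 10-12% error. The documents do not support that, for four reasons.

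1. The cancellation argument needs baseline to be a response. Section 10.4 calls baseline as a covariate the usual choice. In that form an HSC intercept does carry centre differences in baseline-adjusted dmfs, and the error is 5.0% if those differences are constant over follow-up.
2. The random-slope model is offered as an example, the sentence on clustering does not say intercept, and the covariance structure is left open. An HSC slope or HSC-by-visit term is not ruled out.
3. No ICC for change is given. If HSCs do not differ in change, there is no inflation under any of these models.
4. Linear divergence of HSCs through year 3 is an assumption. Children age out of Head Start, and section 4 places the third assessment up to 18 months after the intervention ends.

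All four stand, and they make the size conditional. They do not remove the point. Calling a practice customary does not prespecify it, and the slope example sits in the same paragraph. dmfs is largely cumulative, so centre differences could well widen with time. A standard non-parametric test of change scores, which section 10.4 allows, would ignore clustering; Step 1 is the approximate guide there.

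**Conclusion.** The point holds as a failure to specify the cluster term. It does not establish a known error rate for the planned test. If the optional term is read as an HSC intercept alone, the type I error at 14 per cluster runs from about 5% to about 12%, depending on the role of baseline, whether HSC differences grow, and which visits are modelled. With only years 2-3 modelled it can be near 5% at year 2. If clustering of change is ignored, it is about 12% at 14 per cluster and 15% at 20. All figures above 5% rest on an assumed ICC of change, for which the plan's 0.045 is borrowed. The ranges in Steps 2 and 3 also rest on assumed child-level variances. Because this decides the false-positive rate of the primary test in a cluster-randomised trial, it should be settled before the analysis.

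**What to change.** In section 10.4, replace the sentence on clustering with text that says:

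- HSC, as the randomised unit, is always in the primary model.
- Its effect may differ by visit: an HSC intercept plus an HSC-by-visit effect, or an HSC random slope if time is linear. Alternatively, a separate baseline-adjusted model with an HSC intercept is fitted at each of years 2 and 3.
- Inference uses between-HSC degrees of freedom (for example Kenward-Roger), or HSC-clustered robust standard errors with a small-sample correction.
- Any non-parametric or count-model alternative also accounts for HSC.

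The cost is a few sentences, one or two extra variance parameters and somewhat wider confidence intervals. No change to data collection is needed.

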Two important considerations in fitting mixed models are determining covariance and mean structures for the data. We will first define the covariance structure; many forms are available, depending on the correlations in the data. Little, et al.,³⁴ provide a useful article on modeling the covariance structure for longitudinal data by using the MIXED procedure in SAS software. Once a suitable covariance structure has been determined, an appropriate mean structure can be determined.

Missing or incomplete data are a common problem in randomized clinical trials where the outcome is measured longitudinally. Here, exploratory analyses will be done first to determine if the missing observations are missing completely at random (MCAR), missing at random (MAR), or missing not at random (MNAR) and whether multiple imputation should be done, or modeling of the non-response. Complete case analysis will be the primary analysis,

since available data analysis with mixed models only assumes MAR (Molenberghs). As a secondary analysis multiple imputation or modeling of the non-response mechanism will be done to include those cases without complete data.

The secondary outcomes will include caries patterns, cost analyses and the array of information representing knowledge, attitudes, and behaviors of parents that may serve as mediating and moderating variables. Caries patterns will be analyzed by looking at the different dmfs components and the specific teeth involved.

Cost-effectiveness analysis is used to compare costs of alternative interventions for a similar health outcome. Results are presented as a cost-effectiveness (or CE) ratio of the intervention net cost (intervention costs minus savings) per health outcome such as improvement in quality-adjusted life years (QOL). For this proposal, intervention cost and net cost estimates will be used to construct cost indicators such as the cost/net cost per child served and, if the program is found to be effective, the cost/net cost per unit decrease in caries. Such indicators are sometimes referred to as preliminary CE ratios for 2 reasons. First, the ratios measure the cost for a process-outcome or a health-outcome such as caries rather than QOL. Second, we will estimate only short-term net intervention costs, not long-term costs that may result with improvements in oral health behaviors and practices overtime.

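### Section 10.4 makes complete-case analysis primary for a reason that supports the available-data mixed model, and never defines a complete case

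*Combined protocol and SAP*

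**What the plan says.** Section 10.4 (Final Analysis Plan) defines the primary outcome as the difference between groups in "changes in mean dmfs between baseline and 2-year and 3-year follow-up" and plans linear mixed models with subject-specific effects, baseline as a covariate and a random effect for the randomised group. On missing data it plans an exploratory look at the mechanism and then states: "Complete case analysis will be the primary analysis". The reason attached in the same sentence is that an available-data mixed-model analysis requires no more than MAR. The next sentence reads: "As a secondary analysis multiple imputation or modeling of the non-response mechanism will be done to include those cases without complete data".

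Elsewhere in the document:
- Section 4 (Study Design) also names the increments at both two and three years, and says "Each consented child will participate in the study for up to 3 years".
- Section 8.1 allows each child at most four screenings: baseline and three annual follow-ups.
- Section 10.2 item 7 says "a 70% retention rate was assumed", without naming the visit to which it applies.
- Section 10.2 item 8 makes intention to treat primary and asks children who stop treatment to stay in follow-up. It does not say which children are analysed.

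**The concern.** The reason and the choice point in opposite directions. Needing only MAR is the advantage of fitting the mixed model to whatever follow-up each child has. Restricting the analysis to complete cases gives up that advantage.

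Two things are at stake. First, two statisticians working from Section 10.4 could build different primary datasets, because the method is unclear and a complete case could mean year 2 observed, year 3 observed, both, or all three follow-ups. Second, on the literal reading a child with some follow-up contributes nothing to the primary estimate. If dropout depends on earlier observed dmfs, and does so differently in the two arms, the complete-case estimate can be biased where the available-data estimate would not be.

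**Working it through.** **1. The logic, side by side**

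| Analysis | What it generally needs | Partly followed children | Place in Section 10.4 |
|---|---|---|---|
| Complete cases | MCAR, or missingness depending only on model covariates | left out | primary |
| Mixed model on available data | MAR, with correct mean and covariance models | included | cited as the reason for the primary |
| Multiple imputation or non-response model | depends on the model chosen | included | secondary |

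The property claimed in the second row is used to justify the first.

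**2. Inputs (Section 10.2)**

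52 classrooms of about 20 children, 1,040 enrolled, 70% retention, mean and SD 24, 40% reduction (24 × 0.40 = 9.6 surfaces), intraclass correlation 0.045, alpha 0.05 (taken as two-sided), power 0.80.

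**3. The plan's own figure**

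52 × 20 = 1,040 agrees with the text. The other inputs do not lead to it: 2 × (1.96 + 0.842)² × 24² / 9.6² ≈ 98, or 99 per arm with the t-test. The design effect is 1 + 19 × 0.045 = 1.855. Then 99 × 1.855 / 0.70 = 262.4 per arm, about 525 in total. The Appendix B table is not in the text reviewed, so this is not called an error. It does not affect the counts below, which start from 1,040 enrolled, but it is why no power figure is offered as a measure of harm.

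**4. Children and screenings left out, if 70% is final retention and dropout is permanent**

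Retained: 1,040 × 0.70 = 728. Excluded: 1,040 − 728 = 312.

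Even loss over three years (assumption) means annual retention of 0.70^(1/3) = 0.8879:

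| | Year 1 | Year 2 | Year 3 |
|---|---|---|---|
| Observed | 923.4 | 819.9 | 728.0 |
| Lost since previous visit | 116.6 | 103.5 | 91.9 |

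- No follow-up at all: about 117 children.
- At least one follow-up: 103.5 + 91.9 = 195.4, about 195 children. About 104 have year 1 only and about 92 have years 1 and 2.
- Year-2 and year-3 screenings collected: 819.9 + 728 = 1,547.9. Used by complete cases: 2 × 728 = 1,456. Left out: 91.9, or 5.9%.

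Under permanent dropout, requiring year 3, both years or all visits gives the same 728 children. Requiring only year 2 would exclude 116.6 + 103.5 = 220 children instead of 312.

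**5. Sensitivity to the timing of loss**

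If all 312 are lost before the first follow-up, no collected follow-up screening is left out. If all are lost between years 2 and 3, 312 of 1,040 + 728 = 1,768 year-2 and year-3 screenings are left out (17.6%). Visits missed intermittently would make the loss larger, by an amount the documents do not allow to be estimated.

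**6. Whether bias is possible**

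An illustration with assumed values used independent children, normal data, visit means 12, 16, 20, 24, SDs 14, 17, 20, 24, correlation 0.8 per year apart, a true year-3 difference in change of −6, and 65–68% complete. Dropout depended on the previous observed dmfs. It used 20 runs of 60,000 children per arm (Monte Carlo SE about 0.03). The complete-case estimate is the plain difference in mean change, without baseline adjustment.

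| Dropout | Available-data likelihood | Complete cases |
|---|---|---|
| Unrelated to dmfs | −6.03 | −6.04 |
| Same relation in both arms | −6.03 | −5.94 |
| Related to dmfs in the control arm only | −6.04 | −4.56 |

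This shows that bias can arise, and that it depends on dropout behaving differently by arm. It is not a prediction for this trial.

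**The case against.** The strongest reply is that the sentence is a drafting slip. Section 10.4 says linear mixed models will be used and its reason concerns available data, so the authors may have meant observed data without imputation, with imputation as secondary. That is possible. The next sentence, which brings incomplete cases in only secondarily, favours the literal reading. If it is a slip, the harm is ambiguity alone and the same correction is needed.

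It is also fair to say that the incomplete cases are not ignored, since multiple imputation or non-response modelling is planned for them. That stands. What remains in question is which analysis is primary.

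The size is modest for the stated outcome. With permanent dropout the year-3 contrast has the same 728 observed children either way, and more than half of the partly followed children in the even-loss case have year 1 only.

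A reader might infer four stronger points that the documents do not support:
- **A conflict with intention to treat.** Section 10.2 item 8 concerns following children after treatment stops. It is silent on the analysis set, so there is no contradiction.
- **A conflict with the planned mixed model.** A mixed model can be fitted to complete cases; doing so only discards data that it could use.
- **Loss of up to half the follow-up data, with a matching loss of power.** That needs independent 70% attendance at each visit, which the plan does not state.
- **A biased primary result.** Nothing in the documents shows what drives dropout or whether it will differ by arm.

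**Conclusion.** The concern holds. The primary missing-data sentence in Section 10.4 is wrong as written: its reason supports the method not chosen, the next sentence leaves partly followed children to a secondary analysis, and a complete case is undefined. It should be corrected before analysis, although no invalid result is certain.

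The figures of 312 excluded children and 6% of year-2 and year-3 screenings rest on three assumptions: 70% is final retention, dropout is permanent and even over three years, and every child has three scheduled follow-ups. The last is uncertain, because Sections 4 and 8.1 word participation and screenings as maxima. The gain from correction is mainly validity under MAR. A material gain in power is not claimed.

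**What to change.** Replace the complete-case sentence in Section 10.4 with:

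> The primary analysis is a likelihood-based linear mixed model using all available follow-up dmfs from every enrolled child with a baseline and at least one follow-up screening, analysed in the arm to which the HSC was randomised, with baseline dmfs as covariate, within-child correlation and a random HSC effect; it is valid under MAR if the mean and covariance models are correctly specified.

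In addition:
- If one of the count models allowed in Section 10.4 (negative binomial, ZIP, ZINB) is used instead, fit it to the same analysis set with child and HSC random effects. Any non-parametric test is a sensitivity analysis only.
- Make complete-case analysis a sensitivity analysis, with completeness defined by visit.
- Keep multiple imputation or modelling of non-response (missing not at random, MNAR) as sensitivity analyses that also cover children with no follow-up.
- State the primary analysis set in Section 10.2 item 8.

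The cost is one replaced sentence, one definition, one added line and slightly more analysis work, with no new data. The change does not recover children with no follow-up, does not remove bias under MNAR, and does not settle whether the 2-year or the 3-year contrast is primary.
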